## 1.5 OVERALL SYNOPSIS OF THE CLINICAL INVESTIGATION

ANSM registration #:	2022-A01183-40		
Clinical investigation plan #:	22E0978		
Title of the clinical investigation:	SAFETY AND EFFECTIVENESS CLINICAL EVALUATION OF THE RANGE OF INJECTABLE MEDICAL DEVICES FILLGEL IN FACIAL AESTHETIC TREATMENT		
Sponsor:	KYLANE LABORATOIRES SA [name] SWITZERLAND		
Development phase	Exploratory study		
Objectives:	The primary objective is to evaluate the effectiveness of the FILLGEL range used on different treated zones one month (M1) after treatment using clinical evaluation of the global aesthetic improvement (GAIS) rated by the independent investigator.		
	
 
The secondary objectives of the study are to collect data for the FILLGEL range on: 
 
the effectiveness of the range used on different treated zones six months (M6) and twelve months (M12) after treatment using clinical evaluation of the global aesthetic improvement (GAIS) rated by the independent investigator.
 
the safety using clinical evaluation of the Injection Site Reactions (ISR) rated by the subject and the investigator, and by collection of adverse events (AEs) at M1, M6 and M12.
 
subject's satisfaction and subject's opinion on aesthetic improvement on the different treated zones using clinical evaluation of the GAIS at M1, M6 and M12.
 
the injector's satisfaction on the injection quality using subjective evaluation questionnaire,
 
 
 
Another objective will be to illustrate the device effectiveness by realization of face macrophotographs.
 
		
Design:	
 
Open study,
 
intra-individual,
 
single dose,
 
single centre.
 
		
Planned Sample Size:	
 
68 subjects in total divided in 4 subgroups of 17 subjects, according to the kind of filler injected:
 
Group 1: 17 subjects treated in peri-oral lines by FILLGEL 0
 
Group 2: 17 subjects treated in nasolabial folds and/or in lips by FILLGEL 1 (with at least 10 in nasolabial folds and 7 in lips, both indications possible on the same subjects).
 
Group 3: 17 subjects treated in cheek/cheekbones by FILLGEL 2.
 
Group 4: 17 subjects treated in cheek/cheekbones and/or chin by FILLGEL 3 (with at least 10 in cheeks/cheekbones and 7 in chin, both indications possible on the same subjects).
 
		
Number of investigational study sites:	1 (Eurofins Dermscan Pharmascan)		

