Endpoints:	Proportion with the ov independen An improve	Primary endpoint: Proportion of subjects having an improvement of the zone treate with the overall FILLGEL range of devices as assessed by the independent investigator, one month after treatment, using the GAI An improvement is defined as a subject with "very much improved "much improved" or "improved" score on the GAIS.		
		ty of the FILGEL range ar	nd of each FILLGEL device	
	(IS mo • col inv mo	
 
independently will be assessed by:
 
collection of immediate and early Injection Site Reactions (ISRs) by the subjects on a daily-log every day up to one month after treatment.
 
collection of immediate and early ISRs by the independent investigator immediately and one (M1), six (M6) and twelve months (M12) after treatment.
 
collection of AEs throughout the study.
 
Proportion of subjects having an improvement of the zone treated with the overall FILLGEL range of devices as assessed by the independent investigator, six and twelve months after treatment, using the GAIS.
 
		
	with the ov independer			
	with each F assessed B	- Proportion of subjects having an improvement with each FILLGEL device for the four indication assessed by the independent investigator, or months after treatment, using the GAIS.		
	with the F	- Proportion of subjects having an improvement of the zone trea with the FILLGEL range of devices overall as assessed by subjects, one, six and twelve months after treatment, using the GA		
	with each F assessed	
 
Proportion of subjects having an improvement of the zone treat with each FILLGEL device for the four indications independently assessed by the subjects, one, six, and twelve months at treatment, using the GAIS.
 
Evaluation of the effectiveness on wrinkles/lines filling of the dev FILLGEL 0 used in the peri-oral lines as assessed by the independent investigator one, six and twelve months after treatment using the Bazin Upper lip wrinkles scale.
 
		
	FILLGEL ( independer			
	1 used in	the nasolabial folds as as one, six and twelve month	s filling of the device FILLGEL sessed by the independent ns after treatment, using the	
	FILLGEL 1		olume increase of the device the independent investigator ent, using the Rossi scale.	

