	FILLGEL 2 independer	- Evaluation of the effectiveness on volume restauration of the FILLGEL 2 used in the cheeks/cheekbones as assessed independent investigator, one, six and twelve months after treat using the Ascher lipoatrophy scale.		

🚯 eurofins	Dermscan	PRM03-F-227_V6_EN
	Pharmascan	Clinical investigational plan for MD

KYLANE LABORATOIRES SA	FILLGEL CIP #22E0978	Final version 2.0 Date: 21/09/2022	Confidential Page 16/74
	FILLGEL 3 independent	- Evaluation of the effectiveness on volume restauration of the device FILLGEL 3 used in the cheeks/cheekbones as assessed by the independent investigator, one, six and twelve months after treatment, using the Ascher lipoatrophy scale.	
		atisfaction on the injection mmediately after injection o	quality using a questionnaire n D0.
		of the treatment effect one ompared to baseline by pho	, six and twelve months after tographs taking.
Study Procedures:	Screening, [	00, D7 (phone call for safet	y), M1, M6, M12
Statistical methods:	The statistic	al analysis will be performe	d by the CRO biostatistician.
	on the ITT a The analysi performed o	The analysis of the primary performance parameter will be performed on the ITT and PP population. The analysis of the secondary effectiveness parameters will be performed on the ITT and PP population. In case the ITT and PP population differ by less than 10%, only the PP population will be	
	The analysis the "safety"		ameters will be performed on
	subject's ch	A descriptive analysis of the population will be performed, includin subject's characteristics, subject's disposition, deviations to the protocol, injections characteristics.	
	For the prin	For the primary evaluation criteria:	
	For the para after injectio	For the parameter GAIS investigator with the 5 level scores (at D after injection, M1, M6 and M12), the frequencies and percentage will be presented for the overall face score and for the scores b	
	GAIS subje (1=Improver Improved) au parameters	Two derived parameters will be defined based on the parameters GAIS subject and investigator as a scores of 2 levels (1=Improvement (Very much improved, Much improved and Improved) and 2=No change or worsening). At each time point, these parameters will be described in frequencies, percentages and Confidence Interval (CI) 95%.	
	Inferential a	analysis for the primary ev	valuation criteria

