	the GAIS In 50% will be	For the new derived parameters at M1 (1 month after injection) for the GAIS Investigator, a binomial exact test (bilateral approach) vs 50% will be applied at each time point for the overall face score . This test will compare the proportion of improvement to 50%.	
	For the sec	ondary evaluation criteria	:
	All the varial to their type Statistical te	All the variables will be described using adapted statistics according to their type (quantitative data or qualitative data). Statistical tests will be performed, to assess the change from baseline (Wilcoxon signed rank test).	
	The bilateral	l approach will be used with	a significance level of 0.05.

🔅 eurofins   Dermscan	PRM03-F-227_V6_EN
Pharmascan	Clinical investigational plan for MD

KYLANE	FILLGEL		Final version 2.0	Confidential
LABORATOIRES SA	CIP #22E0978		Date: 21/09/2022	Page 17/74
Estimated dates of the	Estimated dates of the study:		tigation beginning: Q4 202 tigation end: Q4 2023/Q1 2 truitment period duration: 3 tigation overall duration: 12 subject: 12 months + screer	2024 months months + recruitment period

🛟 eurofins	Dermscan	PRM03-F-227_V6_EN
	Pharmascan	Clinical investigational plan for MD

KYLANE	FILLGEL	Final version 2.0	Confidential	
	CIP #22E0978	Date: 21/09/2022	Page 18/74	
LABORATOIRES SA	CIF #22E0978	Date. 21/09/2022	Fage 10/74	

FLOW-CHART							
Procedure	Visit 1 Screening	Visit 2 Day 0	Phone call Day 7	Visit 3 M1	Visit 4 M6	Visit 5 M12	
Days	D-x	D0	D7 ± 1	D30±7	D180±14	D365±14	
Informed consent form signature	•						
Medical examination	•						
Medical history and previous and concomitant treatments collection	•						
Verification of the inclusion and exclusion criteria	•						
Urinary pregnancy test (for women with childbearing potential)		●p					
Confirmation of eligibility		●b					
Photographs (full face + 2 profiles)		●b		•	•	•	
Scoring of effectiveness using specific scales		●b		•	•	•	
Injection		٠					
Injector satisfaction questionnaire		●a					
GAIS live assessment by the independent investigator		●a		•	•	•	
GAIS assessment by the subjects				•	•	•	
Distribution of a subject daily-log	•	•		•	•	•	
ISR collection by subject		Each day di	● uring one month afte the daily-log	r injection, on			
ISR investigator		● a		•	•	•	
AE and concomitant treatments and procedures collection	•	•	•	•	•	•	

a : after injection, b : before injection AE: Adverse Event - GAIS: Global Aesthetic Improvement Scale- ISR: Injection Site Reaction

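### Secondary effectiveness is reported on PP alone when ITT and PP differ by less than 10%, so an open study with no control arm drops its less selected result (minor)

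*Combined protocol and SAP*

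**What the plan says.** All references are to Section 1.5, Overall Synopsis.

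- **Statistical methods, primary.** "The analysis of the primary performance parameter will be performed on the ITT and PP population".
- **Statistical methods, secondary.** "The analysis of the secondary effectiveness parameters will be performed on the ITT and PP population". The next sentence makes this conditional: "In case the ITT and PP population differ by less than 10%, only the PP population will be". The extracted text stops there. The missing verb is taken to be 'analysed' or similar, and its absence is not a fault of the plan.
- **Secondary tests.** "Statistical tests will be performed, to assess the change from baseline (Wilcoxon signed rank test"), two-sided at 0.05.
- **Sample size.** "68 subjects in total divided in 4 subgroups of 17 subjects". Two devices cover two zones each. FILLGEL 1 is planned "with at least 10 in nasolabial folds and 7 in lips, both indications possible on the same subjects", and FILLGEL 3 "with at least 10 in cheeks/cheekbones and 7 in chin, both indications possible on the same subjects".
- **Endpoints.** Several secondary endpoints belong to one device in one zone. An example is lip volume with FILLGEL 1, assessed at months 1, 6 and 12 "using the Rossi scale".
- **Design.** The study is open and within-subject, is labelled exploratory, and lists no control group.

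**The concern.** If one of two analysis sets is to be left out, it should not be the less selected one. By its usual meaning, PP removes subjects for what happened after enrolment. The secondary tests compare each subject with their own baseline, so there is no comparator in which a similar selection could cancel out. If the removed subjects did worse than the rest, the estimate rises, and under this rule no ITT figure stands beside it.

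The condition does not guard against that. Two sets can be almost equal in size and still give different answers, most easily in a small zone where one subject carries real weight. At stake are the zone-scale results, including those at months 6 and 12, where deviations have had longest to accumulate.

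**Working it through.** **Inputs.** From the synopsis: 4 groups of 17; minimum zone sizes of 10 (nasolabial folds) and 7 (lips) for FILLGEL 1, and 10 (cheeks/cheekbones) for FILLGEL 3; the 10% limit; Wilcoxon signed rank, two-sided, 0.05. The 7 chin subjects are left out because the endpoint list shows no zone scale for the chin.

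**Assumptions.** 'Differ' means number of subjects; ITT is everyone planned; there is one score per subject; the signed rank test is exact, with zero changes dropped and midranks for ties. The synopsis fixes none of these.

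**Step 1: the plan's own figure.** 4 × 17 = 68, as stated.

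**Step 2: when the rule applies.** The condition is excluded / ITT < 10%.

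| Level at which the 10% is measured | Exclusions that trigger PP only | First count that keeps ITT |
|---|---|---|
| All 68 subjects | up to 6 (6/68 = 8.8%) | 7 (7/68 = 10.3%) |
| Device group of 17 | 1 (1/17 = 5.9%) | 2 (2/17 = 11.8%) |
| Zone of 10 | none | 1 (1/10 = 10.0%) |
| Zone of 7 | none | 1 (1/7 = 14.3%) |

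On the first two readings, a single exclusion that triggers the rule can still be 14.3% of the lip subjects, or 10.0% of the nasolabial-fold or FILLGEL 3 cheek subjects. On the per-zone reading this cannot happen at the minimum sizes.

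**Step 3: what could be lost on a zone scale.** If every non-zero change is one grade, all ranks tie and the exact two-sided signed rank p-value is 2 × Σ C(m, i) / 2^m. Here i runs from 0 to the number of losses, and m is the number of non-zero changes.

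*Lips: 7 subjects, 1 excluded, the 6 retained each gain one grade.*

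- PP: mean 6/6 = 1.00; p = 2 × 1/64 = 0.031.
- ITT, excluded subject also gains: mean 7/7 = 1.00; p = 2 × 1/128 = 0.016.
- ITT, excluded subject unchanged: mean 6/7 = 0.86; p = 0.031.
- ITT, excluded subject one grade worse: mean 5/7 = 0.71; p = 2 × (1 + 7)/128 = 0.125.

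*Group of 17: 2 excluded; of the 15 retained, 12 gain one grade and 3 are unchanged.* The rule applies here only if the 10% is taken over all 68.

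- PP: mean 12/15 = 0.80; p = 2 × 1/4096 = 0.0005.
- ITT, one gains and one unchanged: mean 13/17 = 0.76.
- ITT, both unchanged: mean 12/17 = 0.71; p = 0.0005.
- ITT, both one grade worse: mean 10/17 = 0.59; p = 2 × (1 + 14 + 91)/16384 = 0.013.

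In these examples the mean falls whenever the excluded subjects did worse. The verdict at 0.05 changes in one case only: 7 lip subjects with the excluded one worse than baseline.

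**The case against.** The strongest reply is that the zone figures depend on a reading the plan does not state. Secondary results are given per device and per zone, so the 10% may be meant at that level. Per zone, the lip example disappears because 14.3% keeps ITT. Per device group, the 2-of-17 example disappears because 11.8% keeps ITT, although the lip example survives at 1/17. If 'differ' referred to results, which is less natural, the lip gap of 1.00 against 0.71 (29%) would also keep ITT. This stands, and it is why every level is shown. It does not remove the point: on each reading, once the condition is met, no ITT result is reported.

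Second, the harm may be nil. Subjects who leave PP because they missed a visit have no change score, so an observed-case ITT analysis would equal PP; nor is anything lost if excluded subjects did as well as the rest. That also stands. But only the ITT result would show it: the planned description of disposition and deviations gives counts and reasons, not those subjects' outcomes.

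Third, the study is exploratory, the rule is prespecified, and without randomisation ITT has no balance between arms to protect. All true; these facts limit the severity. The concern is selection of subjects, not loss of a randomised comparison.

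A reader might go further and infer that the GAIS results at months 6 and 12, or those rated by subjects, are also reduced to PP. The documents do not settle this. The objectives and endpoints treat them as secondary, but the statistical methods describe them under the primary criteria, and the primary parameter is analysed on both populations. No GAIS figures are therefore given.

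**Conclusion.** The point holds as a minor one. The plan removes the less selected secondary effectiveness result because two sets are close, and closeness in size is not evidence that they agree. The size is small to moderate: no effect if excluded subjects have no rating or did as well as the rest, a modest drop in the mean if they did worse, and a changed verdict only in the small lip zone when the excluded subject worsened.

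This rests on the usual meanings of ITT and PP, on 'differ' meaning number of subjects, and on the 10% being measured over all 68 or per device group. The available text is the synopsis, so definitions missing from it are not counted as a fault.

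Two stronger inferences are not supported. The month 1 primary analysis is not weakened, since it is planned on both populations. Nor do the documents show that the secondary results will in fact be overstated: they give no expected exclusions and no outcomes for excluded subjects.

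**What to change.** Delete the 10% condition and state:

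> All secondary effectiveness endpoints are reported on both the ITT and PP populations, whatever the difference between them, and the number of subjects excluded from PP is given per device and per treated zone.

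The fault does not require naming ITT as the main analysis; it is enough that both results are shown. With the condition gone, what the 10% was measured on no longer matters.

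Cost: one sentence of wording, no extra data and no change to the 68 subjects. The downside is a second set of secondary tables and possibly slightly less favourable results.

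### Does the conflict between M1 and each time point leave the investigator GAIS analysis at M6 and M12 open in a way that matters?

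*Combined protocol and SAP*

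**What the plan says.** All references are to section 1.5 of the combined protocol and SAP (overall synopsis) and the flow-chart that follows it.

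- **Primary objective and endpoint:** the proportion improved on the investigator's GAIS one month after treatment, for the whole range of devices.
- **Secondary objective:** "the effectiveness of the range used on different treated zones six months (M6) and twelve months (M12) after treatment using clinical evaluation" on the GAIS. The matching secondary endpoint is the proportion improved as judged by the "independent investigator, six and twelve months after treatment, using the GAIS".
- **Statistical methods, primary evaluation criteria:** the five-level investigator GAIS is tabulated at D0 after injection, M1, M6 and M12. A two-level score is derived for both the investigator's and the subject's GAIS. "At each time point, these parameters will be described in frequencies, percentages and Confidence Interval (CI) 95"%.
- **Inferential analysis for the primary criteria:** "at M1 (1 month after injection) for the GAIS Investigator, a binomial exact test (bilateral approach) vs 50% will be applied at each time point", on the overall face score.
- **Secondary evaluation criteria:** "Statistical tests will be performed, to assess the change from baseline (Wilcoxon signed rank test"). Tests are two-sided at 0.05.
- **Flow-chart:** the row "Scoring of effectiveness using specific scales" carries mark b on Day 0. The row "GAIS live assessment by the independent investigator" carries mark a. The footnote reads "a : after injection, b : before injection".

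**The concern.** The sentence on the binomial test names M1 and then every time point, and both cannot govern. If every time point governs, M6 and M12 are tested against 50%. If M1 governs, those visits appear to pass to the rule for secondary criteria, where the only named test is a Wilcoxon signed-rank test of change from baseline. That test does not fit: GAIS is itself a rating of improvement, and none is scheduled before injection. It could be run only against a score of no change, or against the D0 rating made after injection.

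These analyses ask different questions. With 68 subjects and nobody rated worse, a signed-rank test against no change is significant from 6 improved, while the binomial test favours the device only from 43. If the choice were truly open, the same M6 or M12 data could be reported as effective or as not shown, and the choice could be made after the data were seen.

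**Working it through.** **Inputs.** n = 68 (four groups of 17; 4 × 17 = 68), null proportion 50%, two-sided 0.05, all from section 1.5. The supplied pages give no expected improvement rate, power or loss allowance. I assume 61 subjects seen (about 10% loss) as a second case.

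**Step 1: which analyses does the text support at M6 and M12?**

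- The part headed for the primary criteria is arranged by instrument, not by rank of endpoint. It covers investigator GAIS at all four visits and also subject GAIS, which is only a secondary endpoint. GAIS at M6 and M12 therefore has its analysis there: frequencies, percentages and a 95% CI.
- The Wilcoxon sentence concerns change from baseline. The specific scales have a score before injection; GAIS does not. The M6 and M12 endpoint is a proportion, which is not the kind of quantity that test addresses. The missing baseline is evidence that the test was meant for the scales.
- Neither a signed-rank test against no change nor the use of the D0 rating as a baseline appears in the supplied pages.

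Two readings remain: exact binomial test plus 95% CI, or 95% CI alone.

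**Step 2: do the two readings lead to different conclusions?**

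With X the number improved, the exact two-sided p-value against 50% is 2 × P(X ≥ k | n, 0.5) for k above n/2, and the mirror image below. The Clopper-Pearson lower limit exceeds 50% when P(X ≥ k | n, 0.5) < 0.025, which is the same condition.

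| Improved | Exact p | Clopper-Pearson 95% CI | Wald 95% CI |
|---|---|---|---|
| 43/68 (63.2%) | 0.0385 | 50.7% to 74.6% | also excludes 50% |
| 42/68 (61.8%) | 0.068 | 49.2% to 73.3% | 50.2% to 73.3% |
| 26/68 (38.2%) | 0.068 | 26.7% to 50.8% | 26.7% to 49.8% |
| 39/61 (63.9%) | 0.040 | 50.6% to 75.8% | also excludes 50% |
| 38/61 (62.3%) | 0.072 | 49.0% to 74.4% | 50.1% to 74.5% |

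Across all counts from 0 to 68 and from 0 to 61, the Clopper-Pearson interval and the exact test never disagree. The Wald interval, p̂ ± 1.96 × √(p̂(1 − p̂)/n), disagrees at 42 and 26 of 68, and at 38 and 23 of 61, and nowhere else.

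**Step 3: number of tests.** Testing M1, M6 and M12 makes three tests at 0.05, with a summed bound of 0.15; adding D0 makes four and 0.20. These bounds would matter only if success at any visit counted as success of the study. The objectives and the primary endpoint fix M1, so the primary test stays at 0.05 (attained 0.0385 with 68 analysed).

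**Step 4: the large discrepancy.** With nobody worse, the signed-rank p-value against no change is 2 × 0.5^k: 0.0625 at k = 5 and 0.031 at k = 6. It therefore disagrees with a favourable binomial result at every count from 6 to 42. At assumed true rates of 50%, 60%, 70% and 80%, P(6 ≤ X ≤ 42) is 98%, 66%, 9% and 0.04%. The arithmetic is right, but it compares the binomial test with an analysis that Step 1 does not find in the supplied pages.

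**The case for a change.** The strongest case for a change is that the sentence contradicts itself, concerns the first secondary objective listed, and is followed by a Wilcoxon rule that is not expressly limited to any scale. An exploratory label does not excuse unclear wording, and a few words settled before the data are seen would remove any later choice. The interval method is also unnamed in the supplied pages, and at 42/68 that decides whether 50% lies inside.

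What stands is that the wording is loose, that those pages do not say whether M6 and M12 carry a p-value, and that the interval method is not stated. What does not stand is the consequence. Reading the Wilcoxon rule onto GAIS means ignoring both its reference to baseline and the flow-chart. Without it, the two readings share the same estimate and interval. The Wald point is real but confined to one favourable count and its mirror, and an analyst running an exact test would naturally pair it with an exact interval.

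**Conclusion.** No change to the plan is needed. The conflict between M1 and each time point is a drafting slip that an analyst can resolve sensibly, and either resolution suits an exploratory study. The M1 primary test is untouched. At M6 and M12 the improved proportion and its 95% CI are reported under both readings, and the comparison with 50% comes out the same at every count if the interval is Clopper-Pearson. With a Wald interval it differs at two of the 69 possible counts when n = 68, and at two of 62 when n = 61.

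This rests on two assumptions: that the Wilcoxon test is for the scales scored before injection, which is the natural reading of the flow-chart; and that M6 and M12 stay secondary, as the endpoints state. Only the synopsis and flow-chart (pages 12 to 18 of 74) were available, so a fuller statistical section may already settle the wording.

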🛟 eurofins	Dermscan	PRM03-F-227_V6_EN
	Pharmascan	Clinical investigational plan for MD

KYLANE LABORATOIRES SA	FILLGEL CIP #22E0978	Final version 2.0 Date: 21/09/2022	Confidential Page 13/74	
Inclusion criteria:	
 
3. Age: bet
 
4. Subject s filler. 
 
*For gro
 
(score 3)
 
*For gro
 
(score 3)
 
1 or 2 for seeking s 
 
*For gro
 
cheeks/c
 
lipoatrop
 
*For gro
 
cheeks/c
 
lipoatrop
 
*For gro
 
cheeks/c
 
lipoatrop
 
enhance
 
 
 
5. Subject s 
 
who agre
 
6. Subject s
 
9. Women method througho
 
 
 
In terms of p 
 
1. Pregro
 
the s
 
2. Subject s
 
adm
 
gual
 
3. Subject s
 
Subject s
 
5. Subject s
 

	e or female. ween 18 and 65 years. seeking an improvement of up 1 : Subject with moderat to 5 on Bazin Upper lip sca up 2 : Subject with moderat to 4 on WSRS scale) and/o or superior and/or inferior an improvement of lip volun roup 3: Subject with theekbones volume deficit hy scale); roup 4: Subject with theekbones volume deficit hy scale) and/or subject so ment. whose weight did not fluctu ees to keep a stable weight having given their free, expr psychologically able to up o the study, and to give their registered with a social secu of childbearing potential so considered effective since ut the study. opulation gnant or nursing woman or p study. ject who had been depu inistrative or legal decordianship. ject in a social or sanitary e ject suspected to be non- stigator's judgment. ject having received a pensations for their partici ian beings in the last 1 cipation in the present stud	Page 13/74 her/his face aspect with HA te to severe peri-oral lines e); e to severe nasolabial folds subject with thin lips (score p on the Rossi scale) and e; moderate to severe (score 3 to 4 on Ascher eking improvement of chin ate in the last 6 months and during the study. ess, and informed consent. nderstand the information written informed consent. nderstand the information written informed consent. rity scheme. hould use a contraceptive e at least 4 weeks and during a pregnancy during ved of their freedom by sion or who is under stablishment. compliant according to the total of 4.500 euros as pation in research involving 2 months, including their A yor whose non-enrollment ir or any other lesion on the	

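### Does scheduling no scale score at screening leave the change-from-baseline scale tests open to regression to the mean?

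*Combined protocol and SAP*

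**What the plan says.** All references are to the combined protocol and SAP, section 1.5 (overall synopsis) and its flow-chart.

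- **Entry.** Inclusion criterion 4 sets grade windows: Bazin 3 to 5 (Group 1), WSRS 3 to 4 and/or Rossi 1 or 2 (Group 2), and for cheeks and cheekbones in Groups 3 and 4 "moderate to severe (score 3 to 4 on Ascher". It names no visit and no rater. Chin enhancement has no scale window.
- **Outcomes.** The same four scales are secondary effectiveness endpoints at M1, M6 and M12, rated by the independent investigator.
- **Schedule.** "Verification of the inclusion and exclusion criteria" is marked at screening only. "Confirmation of eligibility" is marked at D0 before injection. "Scoring of effectiveness using specific scales" is marked at D0 before injection, M1, M6 and M12, with no mark at screening.
- **Analysis.** For the secondary criteria: "Statistical tests will be performed, to assess the change from baseline (Wilcoxon signed rank test", two-sided at 0.05.
- **Numbers.** There are four groups of 17. Group 2 is filled "with at least 10 in nasolabial folds and 7 in lips" and Group 4 "with at least 10 in cheeks/cheekbones and 7 in chin", so 17 per scale is assured only for Groups 1 and 3.
- **Status.** The study is labelled exploratory and is open, intra-individual and single-centre. All four groups are treated.

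**The concern.** When subjects are admitted because a noisy rating falls in a window, and that rating is also the baseline, a later rating tends to move back towards the mean of the population they came from. Where candidates typically sit on the milder side of the window, this movement looks like improvement. With no control arm it cannot be separated from the effect of the filler.

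The flow-chart appears to create this situation. The only scheduled pre-injection score is at D0, in the same column as the confirmation of eligibility, so one rating might do both jobs. At stake would be the size of the reported change on the four scales, and the tests of small residual effects, chiefly at M12. A change of one grade or more would exceed the drift. The primary GAIS test against 50% uses none of these scores, and chin treatment has no scale outcome.

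**Working it through.** **1. What the schedule implies.** Criterion 4 is a set of numeric grades, and the criteria are verified at screening, so someone must grade the subject at that visit. The row without a screening mark is the one for effectiveness scoring, that is, outcome data. Its missing mark means the screening grade is not listed as an effectiveness measurement. It does not mean that no grading takes place. The D0 row is a confirmation, placed beside the urinary pregnancy test, and nothing says that it re-applies the grade window. Three readings are possible:

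- A: screening decides and D0 is a separate baseline;
- B: both grades must qualify;
- C: the D0 grade alone decides.

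A fits the rows best and B is possible. C leaves the screening verification with nothing to verify for criterion 4.

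**2. Size under each reading.** The plan gives no figure to reproduce here, and no spread, rater reliability or candidate distribution. Assumed inputs: no treatment effect; true grade normal with SD 0.9; independent rating error with SD 0.35 or 0.7; rating = true grade + error, rounded and held to a 1 to 5 scale; entry window 3 to 4 (WSRS, Ascher). Drift = mean of (D0 grade − follow-up grade) among those admitted; positive means apparent improvement.

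| Candidate mean | C: D0 alone (error SD 0.35 / 0.7) | B: both qualify (0.35 / 0.7) | A: screening alone |
|---|---|---|---|
| 2.5 | 0.158 / 0.342 | 0.092 / 0.229 | about 0 |
| 3.0 | 0.076 / 0.178 | 0.043 / 0.122 | about 0 |
| 3.5 | 0.000 / 0.021 | about 0 | about 0 |
| 4.0 | −0.077 / −0.135 | towards worsening | about 0 |

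B relative to C: 0.092/0.158 = 58%, 0.229/0.342 = 67%, 0.043/0.076 = 57%, 0.122/0.178 = 69%. Reading B therefore keeps roughly 57% to 69% of the drift under C.

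**3. Effect on the tests under B.** False improvement with the exact signed-rank test at n = 17 (nominal 2.5%), error SD 0.35 / 0.7:

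- mean 2.5: 2.5% / 9.7%
- mean 3.0: 1.3% / 4.0%
- mean 3.5: 0.5% / 0.8%

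Only two of these six cells clearly exceed nominal. At n = 10 one does (4.1%), and at n = 7 none does (at most 0.9%). The normal approximation gives about 3% to 14% at n = 17 for means 2.5 to 3.0. The synopsis does not say which version will be used. Under A the n = 17 rate stays near or below nominal (0.3% to 1.9% exact, at most 2.7% approximate).

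**4. Sensitivity.** A second simulation assumed total SD 1, reliability 0.6 to 0.9 and candidate means of 2 or 3. Under C it gave 0.06 to 0.53 grade for the same window, with two-sided rejection of about 7% to 64% at n = 17. With a separate screening grade it gave a drift of at most 0.01 grade. The size under C is thus set almost entirely by the assumptions. The absence of drift under A holds in both, provided the rating errors at the two visits are independent.

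**5. Cost of ruling out a D0 score check.** If screening alone decides and D0 is rated afresh, 13.6% to 36.2% of admitted subjects have a D0 grade outside the window (means 2.5 to 4.0). For a group of 17: 0.136 × 17 = 2.3 and 0.362 × 17 = 6.2, so about 2 to 6 subjects.

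**The case for a change.** The strongest case for acting is that the remedy is small and the gap is real. A numeric threshold is checked at a visit where no score is listed, the deciding visit and rater are not named, and no control arm can absorb a drift. One flow-chart mark and one sentence would settle it. If the D0 grade does decide alone, the exact test at n = 17 could show false improvement in 2% to 20% of trials at candidate means 2.5 to 3.0, against a nominal 2.5%.

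Part of this stands. The synopsis and flow-chart do not state the rule, and reading B cannot be excluded from them. Two things weaken the rest. The larger figures belong to the reading that fits the schedule least: at a candidate mean of 2.5 it would also have 52% to 54% of candidates failing the window on the day of injection. And the pages to hand are the synopsis and flow-chart (pages 12 to 18 of 74). Visit-by-visit procedures would normally be in the body, so silence in the synopsis is weak evidence that the rule is missing. The synopsis also does not say who verifies eligibility. If that is not the independent investigator who rates the outcomes, the selecting grade and the baseline need not be the same rating even at D0.

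**Conclusion.** The concern does not call for a change. On the most natural reading, a grading at screening decides criterion 4 and the pre-injection D0 score is a separate baseline. That is already the arrangement that protects against regression to the mean, and the drift is then about zero if the errors of the two ratings are independent. What is left is an unstated detail that the study team can settle from the visit procedures. The analyst can take D0 as baseline, since it is the only scheduled pre-injection score.

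If the D0 grade must also qualify, the drift is modest: about 0.04 to 0.23 grade at candidate means 2.5 to 3.0, about zero at 3.5, and towards worsening at 4.0. These values depend on an assumed true SD of 0.9, rating error SD of 0.35 to 0.7 and a 1 to 5 scale, none of which the documents give. Even the direction depends on where candidates sit in the window.

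Going further and barring any grade check at D0 is a trade-off with no clear gain. It would leave about 2 to 6 of 17 treated subjects with a baseline outside the entry window, in order to protect secondary tests that would remain open and uncontrolled in an exploratory study. The primary GAIS comparison is unaffected under every reading.
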